2.3.2.7 Up-Titration

In the analysis of efficacy of the up-titration, only patients whose dose was up-titrated will be included. The analyses will be done with both treated bleeds and all bleeds definitions. Of note, for the interim CSR these analyses will not be performed.

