6.4.1 Efficacy Endpoints

One efficacy objective is to evaluate the clinical effect of prophylactic emicizumab on the number of bleeds over time. *This analysis will be performed for each cohort separately*

as well as overall as appropriate. Another objective is to characterize the efficacy up-titration on an intra-patient level. The comparison between historical and on-study treatment period for bleeds over time will also be evaluated for patients who were previously enrolled in Study BH29768. *These patients will enroll exclusively in Cohort A, therefore this intra-patient analysis will be conducted only in patients receiving the 1.5 mg/kg QW maintenance dose.* The definition of a bleed is described in Section 4.7.8. All definitions (i.e., treated bleeds, all bleeds, treated spontaneous bleeds, treated joint bleeds, treated target joint bleeds) will be evaluated for each of the efficacy objectives.

Characterizing the effect of emicizumab on-study treatment period for bleed over time as well as analyses of up-titration and the comparison between historical and on study treatment period for bleed over time will be performed *for Cohort A and for the overall analysis* using a negative binomial regression model, which accounts for different follow-up times, with the patient's number of bleeds as a function of the time that each patient stays in the study included as an offset in the model.

The number of bleeds will be also annualized (Annualized Bleeding Rate—ABR) *for Cohorts B and C as well as* for each patient using the following formula:

$$\text{ABR} = \left(\frac{\text{Number of bleeds during the efficacy period}}{\text{Total number of days during the efficacy period}} \right) \times 365.25$$

Of note, if the convergence of the negative binomial model is not achieved or is questionable, the efficacy analysis will be based on the ABR (formula just above).

The number of bleeds, sites of bleeds, and types of bleeds will be summarized for all patients and listed for each patient individually. Several exploratory analyses will be conducted to characterize the type, location, duration, frequency, and pattern of bleeds. For continuous endpoints, descriptive statistics will be calculated and categorical endpoints will be characterized through frequency tables.

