The primary analysis for all cohorts will be performed 52 weeks after all patients in the primary population of Cohort A have been enrolled or withdrawn prematurely, whichever occurs first (see Section [2.5](#)). The primary population of Cohort A consists of all patients enrolled prior to the close of enrolment for patients ≥ 2 years of age (up to approximately 60 patients) and is used to define the timing of the primary analysis of the study. The efficacy analysis will evaluate the clinical effect of prophylactic emicizumab on the number of bleeds over time (i.e., bleed rate) and will characterize the efficacy of up-titration on an intra-patient and population level. If no patients < 2 years of age are included in the primary population of Cohort A, the primary analysis will still occur at the specified time; however, enrolment to Cohort A may be left open exclusively for patients < 2 years of age in order to enrol approximately 5 such patients. Note that these patients will be included in the primary analysis of Cohort A regardless of their follow-up time. Additionally, all available data from patients enrolled in Cohorts B and C (regardless of their follow-up time) will be included at the time of the primary analysis.

In order to complement the analysis of Study BH29884 in adult and adolescents with inhibitors an interim analysis will be performed for Study BH29992 at the same time as the primary analysis of Study BH29884. An interim clinical study report (CSR) will be written for Study BH29992, in which some analyses may differ from the final study analyses. These differences are outlined in this SAP.

Other interim analyses might occur at any time in order to support health authorities' requests or submissions.

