2.3 OBJECTIVES AND ENDPOINTS

2.3.1 Efficacy Period for All the Endpoints

The start of the efficacy period for each individual patient is defined as the day of the first emicizumab dose.

The end of the efficacy period is defined as the date of the clinical cutoff or the date of withdrawal from the initial study period (i.e., treatment period according to eCRF), whichever is earlier. For patients who withdraw from the study before reaching the Week 1 visit, the duration of efficacy period is set to 1 day and it starts and ends on the day of enrolment.

For patients whose dose is up-titrated, the bleeds on the up-titrated dose are analyzed separately. The efficacy period on a given up-titrated dose starts with the first day on this dose and ends on the day of the clinical cut-off, the date of withdrawal, or on the last day on this specific dose, whichever is earlier.

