2.3.2 Bleed-Related Objectives and Endpoints

The bleed efficacy objectives for this study are as follows:

- To evaluate the clinical effect of prophylactic emicizumab on the number of bleeds over time
- To evaluate the reduction in bleeding rate on-treatment with emicizumab compared with the patient's historical bleeding rate (intra-patient comparison, only patients in Cohort A who previously participated in the non-interventional study (NIS), as patients enrolled in Cohorts B and C will not have previously participated in the NIS)
- To characterize the efficacy of up-titration on an intra-patient level, based on the number of bleeds over time.

The endpoint is the bleed rate and is defined as the number of bleeds over the efficacy period. Different analyses will be conducted as outlined in the sections below.

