4.1 OUTPUT LAYOUTS

The key output layout is designed to address the study objectives in a flexible manner and provide an overall view of the efficacy and safety of emicizumab for all dosing regimens. The key output layout is as follows:

All patients: these outputs will provide an overall view of all the data collected under emicizumab prophylaxis. Patients will be grouped according to their original maintenance regimen at study entry (QW, Q2W and Q4W) with a total column provided as well.

Listings will include all the data for all the patients with a flag indicating the dose related to each event and the dosing regimen of the patients. As appropriate, outputs will be produced for each dosing regimen separately.

Patients may be allowed to up-titrate their emicizumab dose if they meet the pre-specified criteria as described in the protocol. Patients will be grouped according to their original maintenance dose at study entry.

The data under the new, higher dose will be analysed and reported separately. Additional summaries will be produced for key safety and exposure on all data (i.e., data before and after up-titration).

For Cohort A, the primary set of outputs will include patients from 0 to < 12 years of age. Three additional limited sets of outputs will be produced: one for patients \geq 12 years of age, one for the combined sets (0 to < 12 years of age and \geq 12 years of age) and one for patients \leq 2 years old at time of enrolment.

For Cohorts B and C, only one set of outputs will be produced for each cohort and will include all the patients enrolled in these cohorts.

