4.4 EFFICACY ANALYSIS

The efficacy objectives of this study will be investigated without any formal hypothesis testing. All analyses will be of descriptive nature only.

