4.4.1.2 Intra-Patient Comparison

The definition of treated bleeds and all bleeds is described in Section [2.3.2](#). The analysis methodology is the NB regression model.

This analytic model estimates the rate ratio, λ_t/λ_c , which quantifies the risk of bleeding associated with prophylactic emicizumab (λ_t) in comparison to the historical bleeding events (λ_c). The analysis will be performed overall and for each dose titration.

The treatment effect therein is based on a repeated statement in the model with use of the SAS GENMOD procedure. Bleed rates for prophylactic emicizumab and no prophylaxis and the rate ratio will be presented and include 95% confidence intervals.

The intra-patient comparison will be performed on patients who have been enrolled at least 12 weeks before the cut-off.

For the Interim CSR, individual patient's ABR will be provided in a descriptive manner including the reduction in ABR comparing before and after entering into Study BH29992. At this stage, the patients included in the analysis will have been on the study for at least 12 weeks.

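### SAP 2.3.2.7 names no reference for the up-titration analysis; on its natural same-child reading, selection on recent bleeds favours the higher dose even with no dose effect

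*SAP*

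**What the plan says.** SAP 2.3.2 lists three bleed objectives. The third is: "To characterize the efficacy of up-titration on an intra-patient level, based on the number of bleeds over time". SAP Section 2 words the same aim more broadly, to "characterize the efficacy of up-titration on an intra-patient and population level".

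The analysis itself is in SAP 2.3.2.7: "In the analysis of efficacy of the up-titration, only patients whose dose was up-titrated will be included". That section adds that treated bleeds and all bleeds are both used and that the analysis is left out of the interim study report. It states no reference period, contrast or estimand. SAP 4.2.7 only defines the up-titrated population.

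The nearby text does not fill the gap:

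- SAP 2.3.1: "For patients whose dose is up-titrated, the bleeds on the up-titrated dose are analyzed separately". It defines the period on the higher dose but not where the original-dose period ends for an up-titrated child.
- SAP 4.1: "The data under the new, higher dose will be analysed and reported separately".
- Protocol 6.4.1 assigns negative binomial regression to the on-treatment bleed rate "as well as analyses of up-titration and the comparison between historical and on study treatment period". It also promises a listing for the up-titration period and leaves the detail to the SAP.
- SAP 4.4.1.2, on the comparison with pre-study history: "The analysis will be performed overall and for each dose titration". Its reference is the non-interventional study, and only children from that study enter it.

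The selection rule is in Protocol 4.5.2. A child may be up-titrated, from Week 17 and with Medical Monitor approval, after at least 2 qualifying bleeds in 12 weeks. Qualifying bleeds are counted on the maintenance dose after Week 5.

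**The concern.** An intra-patient statement about efficacy needs something within the child to compare with. Pre-study data in the required detail exist only for the Cohort A children who came from the non-interventional study. For everyone else the only within-child reference is the time on the original dose, which contains the bleeds that made the child eligible. Children without such a run of bleeds are left out. This is regression to the mean by design: the earlier period is chosen because it was bad, and the later one is not.

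A reader of the study report could take the expected fall in bleed rate as evidence that the higher dose works in children. Neither document warns of this. Because the reference is unstated, it could also be chosen after the data are seen.

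**Working it through.** The plan gives no effect size, power or expected rate for this analysis, so there is no figure to reproduce.

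**1. What the trigger selects.** Two bleeds in 84 days is 2/84 × 365.25 = 8.7 bleeds per year. A child with a stable annualized bleed rate (ABR) of 1, 2 or 4 expects 84/365.25 × ABR = 0.23, 0.46 or 0.92 bleeds in 84 days. A child in that range who meets the trigger has had 12 weeks well above its own rate, all on the original dose.

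**2. Null simulation, base case.** Each child has a constant rate drawn from a gamma distribution, and the dose change does nothing (true ratio 1.0).

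- From Protocol 4.5.2: 2 qualifying bleeds within 84 days, counted after Week 5; dose change not before Week 17.
- Assumed: mean ABR 2, dispersion 1, all bleeds qualifying, 7 days from trigger to new dose, 52 weeks of follow-up, triggering bleed counted on the original dose.

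About 31% of children are up-titrated. Their true mean ABR is 3.8, before and after. Against the trigger-window rate that is 3.8/8.7 = 0.44. Higher/original ratios by choice of reference:

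| Reference on the original dose | Within-child | Negative binomial, repeated measures |
|---|---|---|
| Whole period | 0.61 | 0.65–0.66 |
| Maintenance only | 0.55 | 0.60–0.61 |
| Last 12 weeks | 0.42 | 0.42 |

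With the whole period as reference, 77% of up-titrated children show a lower rate on the higher dose. Widening the assumptions (ABR 0.3–8, dispersion 0–3, 25–100% of bleeds qualifying, lag 0–28 days, follow-up 52–104 weeks) gave whole-period ratios of 0.20–0.90 within-child and 0.24–0.94 by negative binomial. All were below 1.

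**3. Trial-sized simulation, no dose effect.** Assumed: 60 children followed 52–80 weeks and 20 followed 26 weeks (Protocol 3.1 gives about 6 months for Cohorts B and C), dispersion 1 or 2, 40% or all bleeds qualifying, 7-day lag, every eligible child approved. Medians over trials with at least 4 up-titrated children, whole original-dose period as reference:

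| Mean ABR | Within-child | Negative binomial | Crude pooled | Mean number up-titrated (40% / all qualifying) |
|---|---|---|---|---|
| 1 | 0.44–0.55 | 0.49–0.68 | 0.52–0.70 | 3.4–3.9 / 12.2–12.3 |
| 2 | 0.62–0.71 | 0.67–0.83 | 0.72–0.94 | 9.4–9.6 / 22.4–25.4 |
| 4 | 0.77–0.84 | 0.82–0.92 | 0.92–1.11 | 18.8–20.5 / 33.9–40.9 |

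At ABR 1 with 40% qualifying, 43–54% of trials have fewer than 4 up-titrated children.

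**4. Why ABR 1 to 4.** This is illustrative only. The entry criterion of 6 (Protocol 4.2) or the pre-prophylaxis median of 28.7 in the cited aPCC study (Protocol 1.3), times one minus the 85.8% mean reduction in Protocol Table 1, gives 6 × 0.142 = 0.85 and 28.7 × 0.142 = 4.1.

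**5. What could change the direction.** If the new dose starts on the day of the triggering bleed and that bleed is counted in the later period, the direction reverses. The approval step makes this unlikely, but the period boundary should be written. Protocol 3.3.1 words the trigger as more than two bleeds, which conflicts with 4.5.2; the two passages must be reconciled. A 3-bleed trigger gave ratios of 0.47–0.57, 0.63–0.78 and 0.78–0.86 at ABR 1, 2 and 4, so the lean does not depend on which wording applies.

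**The case against.** The strongest reply is that no before/after ratio is written. The text says only that higher-dose data are reported separately and listed. If the analysis describes the higher-dose rate alone, or uses pre-study history as reference, this bias does not arise. That stands, so the point is conditional. It does not dispose of it: the objective is intra-patient efficacy, a regression model is assigned to it, and the SAP to which the protocol defers does not say what is compared.

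Second, SAP 4.4 states: "All analyses will be of descriptive nature only". That removes any concern about error rates. It does not remove bias from an estimate.

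Third, the direction depends on the estimator. The crude pooled ratio exceeded 1 in three of the four settings at ABR 4, and Protocol 6.4.1 falls back to annualized rates if the model fails. This stands: the lean is shown for within-child and negative binomial estimates only.

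Fourth, the magnitudes are assumed, no refusal of approval is modelled, and few children may be up-titrated. All true; only a range should be quoted.

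A reader might also infer that the dose-specific ratios in SAP 4.4.1.2 show the same fall. The documents do not support that. The original-dose ratio there naturally covers all children from the non-interventional study, while the higher-dose ratio covers selected frequent bleeders. With no dose effect, the bleed rate of up-titrated children divided by the original-dose rate of all children came out at 2.3–4.1, so the higher dose would tend to look worse.

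**Conclusion.** The point holds in conditional form. The analysis is under-specified, and on its natural reading it leans towards the higher dose when the dose does nothing. Under assumed ABRs of 1 to 4 and a 7-day lag, the within-child ratio is roughly 0.4 to 0.85 where 1.0 is the truth. The lean shrinks as the bleed rate rises. Its size rests on the ABR, the spread between children and the share of bleeds that qualify, none of which the documents give.

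It would go too far to say that the plan commits to a biased ratio, or that every estimator favours the higher dose. The consequence is a misleading description of one of three bleed objectives, minor to moderate. No test is affected.

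**What to change.** In SAP 2.3.2.7, and once in Section 2:

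1. Define the original-dose period as running from the first emicizumab dose to the day before the first up-titrated dose. Keep the up-titrated period as in SAP 2.3.1.
2. Present before and after rates in up-titrated children as a listing or descriptive table only, with no rate ratio offered as evidence of dose benefit. Add the note: *patients selected on bleeds in the earlier period; a fall is expected without any dose effect.*
3. Align the intra-patient and population wording in SAP Section 2 with the intra-patient objective in SAP 2.3.2.

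No such note belongs on the SAP 4.4.1.2 ratios, where the tendency is the other way.

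The cost is a few lines of SAP text and a footnote, with no new data. The downside is that the report carries no headline efficacy ratio for up-titration. A model on all treated patients, with dose level as a time-varying covariate, could serve at most as a sensitivity analysis. It assumes stable individual rates and an approval step that carries no prognostic information, and under no effect it still gave 0.69–0.91 at ABR 0.5 and 0.91–0.99 at ABR 1.

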2.3.3 Health-Related Quality of Life (HRQoL) Objectives and Endpoints

The patient-reported outcome (PRO) objectives and endpoints for this study are as follows:

- Evaluate the HRQoL of children 8-17 years of age according to Haemo-QoL-SF (completed by patients)

The Haemo-QoL-SF is a self-report questionnaire for children. Only patients 8 years of age and above will be assessed for HRQoL with use of this questionnaire, which will be completed by the patients as per the schedule of assessments. The Haemo-QoL-SF is derived from the Haemo-QoL questionnaire, which has been developed in a series of age-related questionnaires to measure HRQoL in children and adolescents with hemophilia.

The Haemo-QoL-SF version contains 35 items, which cover nine dimensions considered relevant for the children's HRQoL (Physical Health, Feelings, View of

self, Family, Friends, Other people, Sports and school, Dealing with hemophilia, and Treatment). The Physical Health scale assesses hemophilia-related symptoms (painful swellings and presence of joint pain) and physical functioning (pain with movement) and is of particular interest given that it has been responsive to change with modifications in treatment regimen ([Santagostino et al. 2014](#)). Items are rated with five respective response options: never, seldom, sometimes, often, and always.

- Evaluate proxy-reported HRQoL and aspects of caregiver burden using the Adapted InhibQoL including Aspects of Caregiver Burden questionnaire for all children (completed by caregivers)

This will be completed by caregivers as per the schedule of assessments for all children regardless of age. The Adapted InhibQoL Including Aspects of Caregiver Burden is composed of 32 items that make up 7 domains (Physical Health, Treatment, Perceive condition, Dealing with Inhibitor, Perceive treatment, Family life, Others). In addition, if the child has siblings, there is an additional question that creates 1 domain (Siblings) for a total of 8 domains. All questions on the Adapted InhibQoL are responded to on 5-point scale from 'Never' (1) to 'All the time' (5).

The Physical Health domain consists of five questions focused on the child's hemophilia-related symptoms (bruises, bleeds, painful swellings, presence of joint pain and joint stiffness) and two questions on physical functioning limitations (pain with movement, sleep through the night because of pain) because of hemophilia. Two other domains cover issues related to the burden on caregivers of dealing with a child with inhibitors. The Dealing with Inhibitor domain includes questions on the psychological impact (anxiety, fear and worry) associated with their son's hemophilia A. Additionally, the Perceive treatment domain includes questions focused on the impact that treatment has on the caregiver in terms of the interference with daily life, difficulty in preparing the injections, and satisfaction with the amount of time to administer treatment. These three domains are of particular interest given the consistency with the Haemo-QoL-SF (for Physical Health) and the potential reduction in burden as a result of emicizumab treatment.

- Assess the number of days missed from daycare/school (completed by caregivers) and days hospitalized

Caregivers will be asked to report as per the schedule of assessments the number of days of daycare/school that were missed and this will be completed following the Adapted InhibQoL including Aspects of Caregiver Burden questionnaire. The number of days the child was hospitalized (if applicable) will be derived from data collected on eCRF.

Of note, the Haemo-QoL-SF, caregiver-reported HRQoL, and aspects of caregiver burden questionnaires are completed every 3 months from the Week 1 assessment and request inputs from the past 4 weeks.

2.3.4 Pharmacokinetic Endpoint

The pharmacokinetic (PK) endpoint for this study is the exposure (C_{trough}) of emicizumab in patients receiving 1.5 mg/kg QW, 3 mg/kg Q2W, and 6 mg/kg Q4W, assessed prior to drug administration on Day 1 and at the following timepoints:

- Every week during Weeks 1-4 on emicizumab
- Every 2 weeks during Weeks 5-9 on emicizumab
- Every 4 weeks during Weeks 13-37 on emicizumab
- Every 8 weeks during Weeks 41-49 on emicizumab
- Every 12 weeks from Week 57 thereafter while continuing on emicizumab until the end of the study.

Additional PK samples will be taken in patients who require up-titration.

